5.5.3. Supportive Secondary Endpoint(s)

To understand and characterize the vaccine efficacy against any symptomatic infection, as well as under any infection, the following supportive endpoints will be supplemented with the confirmatory secondary endpoints.

The evaluation of secondary endpoints will be done in the per-protocol analysis set in seronegative subjects, with onset at least 14 and at least 28 days after double-blind vaccination. All analyses will be repeated regardless of serostatus.

	Endpoint definition
Mild infection	A subject is considered as an event when the first occurrence of molecularly confirmed COVID-19 case meeting mild definition with onset at least 14 and at least 28 days post double-blind vaccination.
Moderate infection	A subject is considered as an event when the first occurrence of molecularly confirmed COVID-19 case meeting moderate definition with onset at least 14 and at least 28 days post double-blind vaccination.
US FDA Harmonized COVID-19 cases	A subject is considered as an event when the first occurrence of molecularly confirmed COVID-19 case meeting the US FDA harmonized case definition with onset at least 14 and at least 28 days post double-blind vaccination
Viral Load AUC (VL-AUC)	
Area under the viral load-time curve (VL-AUC in \log_{10} copies/ml) of SARS-CoV-2 viral RNA load as determined by quantitative RT-PCR assay of nasal available samples during the COVID-19 episode.
 
Nasal swab samples are taken at the start of the COVID-19 episode and every 2 days thereafter for the next 14 days or until 2 consecutive negative swabs, whichever occurs later.
 
VL-AUC is calculated based on the viral load values until resolution of the COVID-19 episode.
 
In the calculation of the AUC, all available information (date, timing in hours, and minutes as captured in the data base will be used, but the AUC result will be reported in hours), of the assessment, is taken into account.
 
Data handling regarding the following will be added to the Data Presentation Specifications (DPS):
 
 • PCR local lab versus central lab data • saliva • handling of values below LLOQ/LLOD

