	$AUC VL = \sum_{i=2}^T \frac{[VL_{t_i} + VL_{t_{(i-1)}}]}{2} [t_i - t_{(i-1)}]$ 
where
 
t_i = (actual) timepoint i
 
t_{i-1} = (actual) timepoint $(i-1)$
 
T = last timepoint
 
t_1 = first timepoint
 
VL_{t_i} = \log_{10} viral load at (actual) timepoint i
 
$VL_{t_{(i-1)}}$ = \log_{10} viral load at (actual) timepoint $(i-1)$
 
This will be calculated for all subjects with a molecularly confirmed infection.

--	---

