5.5.4.5. AUC viral load

To compare VL-AUC after infection between the active and placebo groups, the exact Wilcoxon Rank Sum test will be performed.

Values below the LLOQ will be imputed with 1 when detected and with 0 when not detected.

These imputations will be used when calculating the AUC based on equation (1). In addition, in case some observations are missing at the first timepoint after infection and/ or the last timepoint after challenge, missing values should be imputed with 0. No other missing values will be imputed.

AUC-VL values will be descriptively summarized (mean, median, SD, SE, range) by randomized group and COVID-19 severity (all symptomatic infections, mild, moderate to severe/critical).

Individual profiles of viral load over time and $\log_{10}[\text{viral load}]$ over time since onset of a COVID-19 episode will be summarized by randomized group and severity of COVID-19.

The vaccine efficacy against AUC-VL will be estimated through the geometric mean ratio of AUC-VL with associated 95% confidence interval.

As the comparison of the AUC VL after infection between the active and placebo groups is based on post-randomization groups, this analysis may not assess the causal effect of the vaccine on viral load. A sensitivity analysis as described by Gilbert et al. (2003) will be carried out. In this sensitivity analysis, a logistic selection bias model is employed to define a causal estimator for the vaccine effect on viral load. The unknown slope (b) of this logistic model determines the amount of selection bias; b is varied over a plausible range of values. For each value of b , a non-parametric estimate of the causal vaccine effect is calculated. A confidence interval and p-values for the appropriate hypothesis of interest are obtained by bootstrap. If $b < 0$, there is a selection bias towards a lower viral load in the vaccine group as compared to the placebo group. When $b = 0$, no selection bias is assumed. The hypothesis of interest is the one-sided hypothesis of a reduction of the viral load. Therefore, values of $b \leq 0$ will be considered (from -5 to 0 in steps of 0.01). The estimate of the causal vaccine effect with its $100*(1-2*\alpha)$ % confidence interval and the p-value for the one-sided hypothesis of a viral load reduction in the vaccine group will be plotted against the assumed value of b .

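### The 'vaccine efficacy against AUC-VL' is a geometric mean ratio of an AUC already built from log10 values, so it is not a percentage reduction in viral load

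*SAP*

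**What the plan says.** SAP section 5.5.3 introduces the endpoint as "Area under the viral load-time curve" and gives its scale as "VL-AUC in \log_{10} copies/ml", with time reported in hours. The integrand of the trapezoid formula is "\log_{10} viral load at (actual) timepoint i", so the log is taken before integration. Swabs are planned at the start of the episode and "every 2 days thereafter for the next 14 days or until 2 consecutive negative swabs, whichever occurs later". The upper limit of integration is the end of the episode: "VL-AUC is calculated based on the viral load values until resolution of the COVID-19 episode".

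Section 5.5.4.5 compares the arms with an exact Wilcoxon rank sum test and adds the effect estimate: "The vaccine efficacy against AUC-VL will be estimated through the geometric mean ratio of AUC-VL with associated 95% confidence interval". Its data handling rules are "Values below the LLOQ will be imputed with 1 when detected and with 0 when not detected" and, for a missing first or last timepoint, "missing values should be imputed with 0". Section 5.6.1.2 repeats the method for mild cases.

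The SAP nowhere defines an AUC of untransformed load, back-transforms the AUC or divides it by duration. Its one stated recipe for a geometric mean, given for the humoral assays in section 5.8.2.4.1, is to average log10 values and back-transform.

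**The concern.** A proportional fall in viral load is a downward shift of the log10 curve. Its effect on an area under that curve is therefore a difference. A ratio of two such areas depends on how high the placebo curve sits, so the same biological effect gives different percentages in populations with different loads.

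The effect of the vaccine on viral load in moderate to severe/critical cases is a listed secondary objective (section 1.1), and the sensitivity analysis in section 5.5.4.5 frames its hypothesis as a reduction of viral load. A percentage labelled vaccine efficacy in that setting invites the reading that load fell by that much. Read so, it would understate the reduction several-fold. The geometric mean also has no value when any participant's AUC is 0, and no rule covers that case.

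**Working it through.** The SAP gives no figure for this endpoint, so there is none to reproduce.

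**Inputs from the SAP:** the trapezoid sum on log10 load, time in hours, swabs every 2 days for at least 14 days (14 × 24 = 336 h), and the 0/1 codes.

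**Assumptions:** placebo level 3 to 8 log10 copies/mL; true effect a uniform drop of 1 log10, which is 1 − 10^(−1) = 90%.

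**1. Constant profiles.** With placebo level L and drop d over 336 h, the AUCs are 336·L and 336·(L − d). Hence 1 − ratio = d/L, while the true reduction is 1 − 10^(−d). At L = 6, d = 1: 2016 versus 1680, ratio 0.83, estimate 16.7%. For d = 1:

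| Placebo level (log10 copies/mL) | 3 | 4 | 5 | 6 | 7 | 8 |
|---|---|---|---|---|---|---|
| Planned estimate | 33.3% | 25.0% | 20.0% | 16.7% | 14.3% | 12.5% |
| True reduction in load | 90% | 90% | 90% | 90% | 90% | 90% |

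**2. The reverse question.** A reported 20% means d = 0.2·L. At L = 4, d = 0.8 and the reduction is 84%. At L = 8, d = 1.6 and it is 97.5%.

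**3. Declining profile.** Placebo starts at 7 log10 and falls 0.35 per day, so its 14-day mean is 4.55; the vaccine curve lies 1 log10 lower, mean 3.55. The AUCs are 4.55 × 336 = 1528.8 and 3.55 × 336 = 1192.8, ratio 0.78, estimate 22%. The difference divided by 336 is 1.0 log10, which back-transforms to 90%.

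**4. With the SAP's codes.** Take the same profile, with assumed limits of 2 log10 (detection) and 3 log10 (quantification). The coded placebo values are 7, 6.3, 5.6, 4.9, 4.2, 3.5, 1, 1 and the vaccine values 6, 5.3, 4.6, 3.9, 3.2, 1, 0, 0. The AUCs are 48 × 29.5 = 1416 and 48 × 21 = 1008. The planned estimate is 1 − 1008/1416 = 29%. The time-averaged difference is 408/336 = 1.21 log10, which gives 94%: near 90% but not exact, because the codes distort the lower part of the curve.

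**5. Reading the ratio as 10^(difference in AUC).** For a 1 log10 drop over 336 h the exponent is −336. This reading works only after division by duration, which the SAP does not do.

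**6. Zero AUC.** If all quantified values are not detected, the coded AUC is 0 and its log is undefined. In a simulation of 4000 participants per arm with the limits in step 4, 2 vaccine participants and no placebo participant had an AUC of 0.

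**The case against.** The best defence is that the label is vaccine efficacy against AUC-VL, and the ratio is exactly a ratio of AUCs. An AUC combines level and duration, so if the vaccine mainly shortens shedding a ratio is a natural summary. The endpoint is supportive, the test is rank-based, and the SAP also plans AUC summaries by arm, load profiles over time, peak load and time to undetectable. The true difference in load would be visible elsewhere. All of this limits the harm. None of it makes the percentage interpretable as an effect on viral load.

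Three stronger readings are tempting and are not supported.

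- A reader might infer that the estimate is arbitrary because it changes with the concentration unit. Without the codes it does: 6 versus 5 log10 copies/mL gives 17%, and the same data in copies/µL (3 versus 2) give 33%. But the SAP fixes copies/ml and codes not detected as 0. With the codes held fixed, simulation under the assumed limits gave 29.4% in copies/mL and 27.5% in copies/L (zero AUCs dropped). The unit illustrates the missing natural zero; it is not the practical problem.
- A reader might infer that the planned AUC can simply be divided by 336 h. It cannot, because integration runs to resolution. Suppose load averages 4 log10 in both arms, for 16 days on placebo and 14 on vaccine. The AUCs are 1536 and 1344, and 192/336 = 0.571 would back-transform to a spurious 73% reduction.
- A reader might infer that any single-sample episode has an AUC of 0. The trapezoid sum alone gives that, but the rule that sets a missing first or last value to 0 can turn a single positive sample into a triangle with positive area. The clear case is all values not detected, which should be rare in molecularly confirmed infections.

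**Conclusion.** The point stands: the planned estimate mixes two scales. For a uniform 90% reduction it returns 12.5% to 33% across assumed constant placebo levels of 8 to 3 log10 copies/mL, 22% for the assumed declining profile, and 29% for that profile once the codes are applied. It is undefined for an AUC of 0. These sizes rest on a uniform shift and on assumed levels and assay limits; the dependence on placebo level follows from the formula alone.

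A reader might infer that the viral load comparison as a whole is invalid. It is not: a further log does not change ranks, so the Wilcoxon test is untouched, as are alpha control and the primary and confirmatory secondary results. The correction is worth making because it is cheap and the number would probably be misread.

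**What to change.** In section 5.5.4.5, replace the geometric mean ratio of AUC-VL as follows.

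- For this estimate only, compute the log10 AUC over a common window, from the first swab (Day 0) to Day 14, instead of to resolution. This is the minimum planned swab period, so the data are already scheduled.
- Divide by the window length (336 h) to obtain each participant's time-averaged log10 viral load.
- Report the between-arm difference (vaccine minus placebo) with its 95% CI, and back-transform it as 1 − 10^difference to give the percentage reduction in geometric mean load.
- State that the 0/1 codes below the LLOQ are on the log10 copies/mL scale. The section does not say, and an untransformed 0 has no log10. Note that the back-transformed percentage is approximate when many values lie below the LLOQ.
- Keep the Wilcoxon test and the descriptive summaries of AUC to resolution, which capture duration. Do not label a ratio of log10 AUCs as vaccine efficacy.
- Carry the change through to the mild-case analysis in section 5.6.1.2.

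The difference remains defined when a participant's AUC is 0. The cost is SAP wording and one extra derivation on a truncated window. The downside is that this estimate does not capture shedding after Day 14.

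### The slope grid for the viral-load AUC selection-bias analysis does not fit an outcome in log10-hours, so nearly all its points lie close to the worst case

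*SAP*

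**What the plan says.** Section 5.5.3 defines VL-AUC as a trapezoid area. The height is log10 "viral load at (actual) timepoint i", actual sampling times are used, and "the AUC result will be reported in hours". Swabs are taken every 2 days for 14 days, or until two consecutive negatives if that is later.

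Section 5.5.4.5 gives the reason for the sensitivity analysis: "As the comparison of the AUC VL after infection between the active and placebo groups is based on post-randomization groups", the comparison may not be causal. It then describes the model: "The unknown slope (b) of this logistic model determines the amount of selection bias; b is varied over a plausible range of values". Only values at or below zero are used, and they "will be considered (from -5 to 0 in steps of 0.01"). The estimate, its confidence interval and a one-sided p-value are to be plotted against b.

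The section does not say that the AUC is standardized, rescaled or log-transformed before it enters the logistic model. It does say, in a separate sentence, that the vaccine effect on AUC-VL is estimated by a geometric mean ratio.

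**The concern.** The slope of a logistic model is a log odds ratio per one unit of the outcome, so a plausible range for b depends on the size of that unit. A range of -5 to 0 suits an outcome with an SD near 1, such as a single log10 viral load. An AUC in log10-hours varies by hundreds of units. On that scale the smallest non-zero step is already strong selection, and the rest of the grid adds almost nothing.

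The viral-load effect is a listed secondary objective. Section 5.5.4.5 concedes that comparing infected participants conditions on a post-randomization event, and this is the only analysis it offers in response. If the plotted curve has one point with no selection and nearly all the others close to the worst case, a reader cannot find the amount of selection at which a reduction would lose support. A real reduction could look fragile only because intermediate degrees of selection were never evaluated.

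**Working it through.** **Inputs from the SAP**
- Grid (Section 5.5.4.5): -5 to 0 by 0.01, so 5/0.01 + 1 = 501 values; smallest non-zero |b| = 0.01.
- Outcome unit (Section 5.5.3): log10 viral load × hours.
- Nominal sampling span (Section 5.5.3): 14 × 24 = 336 h.
- Vaccine efficacy: 60%, the design assumption of Section 3.1, borrowed here to set the share of placebo cases who would also have been cases on vaccine (1 - VE = 0.4).

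The SAP gives no SD of AUC and no expected result for this analysis, so there is no figure of its own to reproduce.

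**Step 1: units alone, no SD needed.** A difference of 1 log10 sustained over 336 h is 336 AUC units. The odds ratio for that difference is exp(336 × b):
- b = -0.01: exp(-3.36) = 0.035
- b = -0.02: exp(-6.72) = 0.0012
- b = -5: exp(-1680)

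**Step 2: distance to the worst case.** Take the placebo-case AUC y as normal with an assumed SD. Set w(y) = expit(a + b·y) and solve a so that the mean of w is 0.4. The adjusted placebo mean is Σwy/Σw. The worst-case bound is the mean of the lowest 40% of y. The table shows the share of the full shift to that bound reached at each b, and the number of the 501 grid points (b = 0 included) below 90% of it.

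| Assumed SD (log10-hours) | SD/336 (log10) | b = -0.01 | b = -0.02 | Points below 90% |
|---|---|---|---|---|
| 50 | 0.15 | 29% | 52% | 8 |
| 100 | 0.30 | 52% | 76% | 4 |
| 150 | 0.45 | 66% | 86% | 3 |
| 200 | 0.60 | 76% | 91% | 2 |
| 300 | 0.89 | 86% | 96% | 2 |
| 400 | 1.19 | 91% | 98% | 1 |
| 600 | 1.79 | 96% | 99% | 1 |

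Simulated episodes with a linear decline and swabs every 2 days (AUC SD about 503) gave 93% and 98% at the first two steps. Varying VE from 50% to 80% changes little: at SD 200 the first step stays at 75% to 76%. Even at SD 50, only 11 of 501 points lie below 95% of the bound, so at least 490 lie at or above it.

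**Step 3: the same grid per SD.** For a normal outcome the share depends only on b × SD. With b defined per SD, the grid reaches 29% of the bound at -0.5, 52% at -1 and 94% at -5, spread across its whole length.

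**Step 4: if the AUC were logged first.** With the simulated episodes and VE 60%, b = -5 reaches about 55% of the bound on log10(AUC) and 82% on ln(AUC). The grid would then stop short of the bound instead of collapsing onto it.

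**The case against.** The strongest objection is that the SAP does not say on what scale the AUC enters the selection model. Hours are given as a reporting unit. The geometric mean ratio is a log-scale measure, and the cited method or its R code, neither of which is available here, might transform or standardize the outcome. This stands as a limit: the collapse shown above is conditional on an untransformed AUC. That is still the plain reading, because Section 5.5.4.5 ties the model to the AUC comparison and states no transformation. Under a log transformation the grid misses the bound, so the scale of b needs stating in either case.

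The SD is also assumed. A reader might infer that all but one or two of the 501 points sit near the bound. The SAP gives no SD to support that as a fact: the count below 90% is 3 at SD 150, 4 at SD 100 and 8 at SD 50.

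Two other inferences go too far. The slope b = -5 is uninformative, not numerically degenerate, because the calculation returns a finite value equal to the bound. It also does not follow from the plan that an observed reduction would change sign at the first step. That depends on the size of the reduction, the SD and the vaccine efficacy, none of which the SAP gives for this endpoint.

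Finally, the harm is bounded. VL-AUC is a supportive secondary endpoint outside the key confirmatory set, the main comparison is an exact Wilcoxon test that the grid does not touch, and a grid that overweights the worst case errs toward caution. All of this is correct and limits the importance of the point.

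**Conclusion.** The concern holds if the AUC enters the logistic model untransformed. The stated grid then does not meet the section's own aim that "b is varied over a plausible range of values". The step from b = 0 to b = -0.01 covers about 66% to 96% of the distance to the worst case for assumed SDs of 150 to 600 log10-hours and VE 60%. Only 1 to 3 of 501 points lie below 90% of the bound, and at most 8 do even at SD 50. The exact count depends on an SD that the SAP does not provide, but the near-flat plot does not: it appears at every SD examined. The odds ratio of 0.035 at the first step needs no SD at all.

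The consequence is an uninformative sensitivity plot for a supportive secondary endpoint. No confirmatory conclusion changes. The correction is worth making because it alters the plotted estimates, intervals and p-values, and because this analysis is the section's only answer to the selection problem it raises.

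**What to change.** In Section 5.5.4.5, state the scale on which AUC-VL enters the logistic selection model (untransformed or logged). Define b per SD of AUC-VL on that scale, by dividing by the pooled SD before fitting. Keep -5 to 0 in steps of 0.01 on the standardized scale, and label the horizontal axis as odds ratio per SD.

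Do not substitute time-averaged viral load to make the existing grid fit. Section 5.5.3 calculates the AUC until the episode resolves, so duration of shedding is part of the endpoint and averaging over time would remove it.

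The cost is about one sentence in the SAP and a rescaling step in the program, if the code does not already standardize. No new data are needed.

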5.5.4.6. US FDA Harmonized definition

Estimating the Vaccine Efficacy (VE) and the associated 95% confidence interval for the US FDA harmonized definition will be done according to the methodology as explained in Appendix 8.

5.5.4.7. Mild Cases

Estimating the Vaccine Efficacy (VE) and the associated 95% confidence interval for participants with an infection that is at most of mild severity will be done according to the methodology as explained in Appendix 8.

5.5.5. Analysis of VE versus placebo for secondary endpoints using data after unblinding

The analysis as described in section 5.4.8 for the primary endpoint will be repeated for the endpoints severe events and FDA definition.

5.6. Tertiary/Exploratory Endpoint(s) Analysis

The potential association between vaccine efficacy and baseline or other potential influential factors (including but not limited to region, age group, comorbidities, Ad26 VNA seropositivity, SARS-CoV-2 seropositivity, profession, smoking status, seropositivity against other coronaviruses and coinfection with any other respiratory pathogens and other risk factors) will be explored by multivariate, covariate-adjusted analyses or subgroup summaries, including 95% confidence intervals.

All exploratory endpoints analysis will occur in the PP analysis set, in seronegative subjects unless otherwise indicated.

Other ad hoc analyses may be performed if deemed appropriate to characterize the safety, immunogenicity and efficacy profile of the vaccine. Post-hoc analyses (analyses performed that are different from this SAP) that are included in the final CSR will be documented in the Changes to Planned Analyses section of the CSR.

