5.4.5. Supportive analyses

The primary analysis will be supplemented with the following analyses.

For subjects with molecularly confirmed COVID-19, the follow-up time is defined as the time between double-blind vaccination and the time of onset of the case. For all subjects without COVID-19, follow-up time is defined as the time since vaccination until the date of unblinding or study discontinuation.

Time to first occurrence of molecularly confirmed moderate or severe/critically ill COVID-19 is defined as the time between double-blind vaccination until onset of the case for the PP set. Subjects without moderate and severe/critically ill COVID-19 are censored at their follow-up time as defined above.

In a supportive analysis of the primary efficacy endpoint, vaccine efficacy will be estimated with an associated two-sided confidence interval (Wald test) based on the hazard ratio obtained from a Cox proportional hazards regression model. The analysis will be stratified for age (≥ 60 yrs, < 60 yrs) and comorbidities (with or without comorbidities). The strata will be based on the values in the database (which may differ to the strata as recorded in IWRS). The alpha-level at the time of crossing the boundary will be used to calculate the confidence interval.

As a supplementary analysis, a Negative Binomial model (using an asymptotic model including estimation of a dispersion parameter) will also be fitted.

The primary and supportive analysis as described for moderate and severe/critically ill COVID-19 cases in the per-protocol population in seronegative subjects will be repeated using the following analysis populations and endpoints:

- FAS, SN (seronegative) with onset of molecularly confirmed, moderate and severe/critically ill COVID-19 one day after double-blind vaccination
- PP, SN subjects with onset of molecularly confirmed, moderate and severe/critically ill COVID-19, at least 28 days after double-blind vaccination, thereby excluding subjects who were seropositive at or before Day 29 based on PCR or serological testing of Day 29 (subjects with missing data will be included)
- PP, SN subjects with onset of molecularly confirmed, moderate and severe/critically ill COVID-19, at least 14 and at least 28 days after double-blind vaccination, thereby excluding subjects with a missing result for the baseline serology sample

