In a subset of participants to further assess the humoral immune response to Ad26.COV2.S, as compared to placebo for functional and molecular antibody characterization including, but not limited to avidity, Fc-mediated viral clearance, Fc characteristics, Ig subclass, IgG isotype, antibody glycosylation, and assessment of antibody repertoire, adenovirus neutralization as measured by VNA, analysis of antibodies to S and the receptor-binding domain (RBD) of the SARS-CoV-2 S protein and SARS-CoV-2 neutralization as measured by virus neutralization assay (VNA; wild-type virus and/or pseudovirion expressing SARS CoV-2 S protein).

To explore changes in the SARS-CoV-2 genome by development of SARS-CoV-2 variants

To evaluate patient-reported outcomes (PROs) in relation to the presence of SARS-CoV-2 infection and the presence, severity and duration of COVID-19 signs and symptoms in participants who received Ad26.COV2.S, as compared to placebo by presence, severity and duration of COVID-19 signs and symptoms and confirmation of SARS-CoV-2 infection by molecular testing.

To assess the difference in severity of cases in participants who received Ad26.COV2.S as compared to placebo by reduction in severity of COVID-19 signs and Symptoms

To assess the impact of pre-existing humoral immunity against coronaviruses other than SARS-CoV-2 at baseline on Ad26.COV2.S vaccine immunogenicity.

To assess the incidence of co-infection of COVID-19 and other respiratory pathogens and to assess the effect of the vaccine during such co-infections as well as to estimate the incidence of other respiratory pathogens during the study period.

To assess the frailty index in participants who received Ad26.COV2.S as compared to placebo.

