6.8. Appendix 8 Statistical Methodology for Poisson Regression

Vaccine efficacy is defined as 1 minus the ratio of the expected incidence rate of cases of COVID-19 in the active group compared to the expected incidence rate in the placebo group.

Vaccine efficacy can be estimated by:

$$\widehat{VE} = 1 - \frac{n_2/N_2}{n_1/N_1} = 1 - \frac{r * n_2}{n_1}$$

Where:

n_2 = number of cases in the vaccinated group

N_2 = follow-up time in the vaccinated group

n_1 = number of cases in the control group

N_1 = follow-up time in the control group

$$r = \frac{N_1}{N_2}.$$

Let $n = n_1 + n_2$ denote the total number of cases. Suppose that $n_i|N_1, N_2 \sim Poisson(N_i p_i)$, $i = 1, 2$, so that $VE = 1 - p_2/p_1$. In this case, conditionally on n and r , n_2 is binomially distributed as $B(n, \pi)$, where $\pi = N_2 p_2 / (N_1 p_1 + N_2 p_2) = (1 - VE) / (r + 1 - VE)$.

Let $q = n_2/n$ denote the proportion of cases in the vaccine group. Then, the vaccine efficacy estimator can be rewritten as:

$$\widehat{VE} = 1 - \frac{n_2}{n} * \frac{r * n}{(n - n_2)} = 1 - \frac{r * q}{(1 - q)}$$

Therefore, there is a monotonically decreasing link between the estimated VE and $q = n_2/n$, the observed proportion of cases in the vaccine group among the total cases, and so rejecting a hypothesis for extreme values of q is equivalent to rejecting that same hypothesis for inversely extreme values of \widehat{VE} .

Given the sequential testing strategy, the confidence interval for the vaccine efficacy will be adjusted accounting for repeated testing. At the primary analysis when the boundary is crossed or at 154 events, the vaccine efficacy estimate will be reported using the estimated VE (as detailed above) at the time of analysis, accompanied with $(1 - 2\alpha^*)\%$ two sided CI, where α^* is the type I error at that time. Using the exact binomial CI for p an (adjusted) exact Poisson regression CI can be constructed (Dragalin et al, 2002; Nauta, 2011). In section X1 the R code to generate the SPRT bounds and to derive the relevant $(1 - 2\alpha^*)\%$ levels is given. The results of the code are presented in [Table 15](#).

1. Section X1: R code SPRT

```

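### SAP section 5.6 lists co-infection, a post-randomization factor that can presuppose COVID-19, as a covariate or subgroup for VE; that analysis cannot show effect modification

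*SAP*

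**What the plan says.** SAP section 5.6 opens with an exploratory analysis of "The potential association between vaccine efficacy and baseline or other potential influential factors". Its examples include region, age group, comorbidities and smoking status, and end with "seropositivity against other coronaviruses and coinfection with any other respiratory pathogens and other risk factors". The method for the whole list is that these factors "will be explored by multivariate, covariate-adjusted analyses or subgroup summaries, including 95% confidence intervals".

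The section does not define co-infection, say who is tested for other pathogens, or fix a risk set. The exploratory objectives in section 5.6.1.1 include this one: "To assess the incidence of co-infection of COVID-19 and other respiratory pathogens and to assess the effect of the vaccine during such co-infections". The same sentence goes on to cover the incidence of other respiratory pathogens during the study. Sections 5.6.1.2 to 5.6.1.4, which give the exploratory methods, contain no analysis of co-infection. Section 5.8.3 does not list it among the subgroups.

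**The concern.** Region, age and smoking status are fixed before vaccination, so randomization balances them and a subgroup VE compares like with like. Co-infection arises later. In the section 5.6.1.1 sense, a participant must already have COVID-19 to have it, so membership of the subgroup depends on the outcome that VE is meant to measure.

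A subgroup made up only of cases has no participants who escaped disease, and its VE carries almost no information about protection. Set beside the remaining participants, whose VE is nearly untouched, it would look as if efficacy disappears under co-infection. No confirmatory test is at stake. What is at stake is a misleading exploratory table.

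**Working it through.** The SAP states no figure for this analysis, so there is none to reproduce. As a check that its binomial framework was read correctly, its design figures were recomputed with pi = (1 - VE)/(2 - VE), which is 0.7/1.7 = 0.4118 at VE 30% and 0.4/1.4 = 0.2857 at VE 60%. The smallest total with exact one-sided alpha at most 0.025 and power at least 0.90 is 154. The efficacy boundary in section 5.9.5 gives alpha 0.02398 and power 0.8622. All agree with section 3.1.

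**Algebra, with cases and follow-up both restricted to the co-infected.**

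1. Appendix 8: "Vaccine efficacy is defined as 1 minus the ratio of the expected incidence rate of cases of COVID-19 in the active group" compared with placebo. The estimator is VE = 1 - (n2/N2)/(n1/N1), with n cases, N follow-up time, 1 = control and 2 = vaccine.
2. Risk scale: every member is a case, so risk is 1 in each arm and VE = 1 - 1/1 = 0 for any true VE.
3. Person-time scale: section 5.4.5 says "For subjects with molecularly confirmed COVID-19, the follow-up time is defined as the time between double-blind vaccination and the time of onset of the case". With m the mean time to onset, N = n x m in each arm, so the rate is 1/m and VE = 1 - m1/m2. The case counts cancel. Only a difference in onset timing between the arms remains.

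**Simulation on the person-time scale.** Inputs from section 3.1: about 40,000 participants randomized 1:1 (20,000 per arm), VE 60%, and incidence falling by 50% in Month 4 and by 62% thereafter. The annualized starting incidence was 1.4% (the planning value) or 5% (assumed, within the 3.8% to 6.3% range quoted for late 2020). Also assumed: 180 days of follow-up and 5% to 20% of cases co-infected. There were 300 replicates per row; those without a co-infected case in both arms were dropped. Entries are median VE in %.

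| Incidence | Co-infected share | True VE | Co-infected subgroup | Not co-infected | Case type, all at risk |
|---|---|---|---|---|---|
| 1.4% | 5% | 60 | -12.2 | 61.1 | 50.1 |
| 1.4% | 10% | 60 | 0.6 | 60.3 | 60.0 |
| 1.4% | 20% | 60 | -1.3 | 60.1 | 60.1 |
| 5% | 5% | 60 | 3.3 | 59.9 | 61.4 |
| 5% | 10% | 60 | 1.1 | 60.0 | 60.7 |
| 5% | 20% | 60 | -1.6 | 60.0 | 59.7 |
| 5% | 20% | 90 | 2.5 | 90.1 | 90.4 |
| 5% | 10% | 0 | -1.5 | 0.3 | 0.0 |
| 5% | 10% | 70 waning to 30 | 16.0 | 54.2 | 55.7 |

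The first row rests on very few events. Expected placebo cases are 20,000 x 0.014 x (91 + 0.5 x 31 + 0.38 x 58)/365, about 99. Of these, 5% is about 5 co-infected on placebo, and 40% of that is about 2 on vaccine. In the waning row the subgroup value rises because vaccine cases occur later.

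**Covariate adjustment.** The indicator equals 1 only in cases. A model for the probability of disease separates. In a rate model, the interaction with vaccine reproduces the onset-time ratio of step 3.

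**Alternative meaning.** If the factor is any other pathogen found irrespective of SARS-CoV-2 status, non-cases enter the subgroup. With 5% of participants positive, independently of arm (assumed), at 5% incidence, a 10% share and true VE 60%, the median subgroup VE was 59.6%.

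**The case against.** The strongest reply is that section 5.6 does not commit the sponsor to the degenerate calculation. It specifies no denominator. Where the SAP reports VE by other features known only in cases, nothing says that the risk set shrinks to those cases: severity in section 5.5.4.2, number of symptoms met in section 5.6.1.3, and variants in section 5.6.1.4, where other participants' follow-up is expressly kept. Read that way, VE by co-infection is VE by case type and is sound. The list openly admits factors that are not baseline. The objective in section 5.6.1.1 also covers other pathogens in general, and section 5.2.4 has symptoms trigger swabs, so swabs from SARS-CoV-2-negative participants may exist. Section 5.8.3 plans no such subgroup.

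Much of this stands. A reader might infer that co-infection can be recorded only in COVID-19 cases, and that a VE of 0% is therefore built into the plan. The documents support neither as a flat statement: who is tested is not given, and the result depends on a risk set that section 5.6 leaves open.

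It does not remove the point. The words in section 5.6 are covariate adjustment or subgroup summary, the same as for age or smoking, and no case-type rule is attached. Admitting non-baseline factors supplies no valid method for them. Section 5.5.4.5 shows that the SAP recognizes the hazard: it warns that a viral-load comparison in groups formed after randomization may not be causal, and it adds a sensitivity analysis. Co-infection gets no such caution.

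**Conclusion.** The point holds in conditional form. Co-infection is post-randomization on every reading, and the method listed for it cannot measure modification of VE. If cases and follow-up are both restricted to the co-infected, VE is exactly 0 on the risk scale. On the person-time scale the median lay between about -12% and 16% in the scenarios run, with true VE from 0% to 90% making little difference. The -12% reflects sparse events and the 16% reflects waning. These values rest on an assumed co-infected share, since the SAP gives none, and on the assumed incidence and follow-up shown.

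It would go too far to say that efficacy under co-infection will be reported as zero. Under a case-type analysis, or if the factor is any other detected pathogen, VE is not forced to 0. It would also go too far to say that section 5.6 is the declared method for the co-infection objective; it is only the one place that attaches a method to the factor. No primary or key secondary test is touched, so this is a minor correction.

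**What to change.** Remove co-infection from the covariate and subgroup list in section 5.6. Add to section 5.6.1.2 an estimate of VE against COVID-19 with a detected co-pathogen and, separately, without one, each as its own case type. Keep the whole per-protocol seronegative set at risk. Include the follow-up of cases of the other type, or with a missing co-pathogen result, up to onset. State who is tested for other pathogens.

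Section 5.6.1.4 already supplies this structure for variants, along with two conditions worth carrying over: a comparable proportion of tested cases in the two arms, and tabulation only when there are fewer than 6 cases.

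The cost is a wording change and one extra exploratory table. Intervals will be wide if co-infected cases are few: at 5% incidence, a 10% share and true VE 60%, the central 95% of simulated case-type estimates ran from 26% to 82%.
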